120 healthy male and female adult subjects will complete the following procedures on two or three separate visits, separated by at least three weeks. A flow chart of the events can be seen in the figure. Using a 64-channel EEG system, peak alpha frequency will be measured while participants undergo a baseline, pain-free resting state (no stimulation), an acute pain resting state, a return from pain resting state, and a neuropathic-like pain (ongoing pain) resting state.

Date: 6/6/2018

Principal Investigator: [name].

Application Number: HP-00064214

Visit 0 is an eligibility screening visit that consists of drug testing (randomly selected with 1/10 probability), a health screening, and quantitative sensory testing (QST) with thermal stimulation by machine and capsaicin cream application. Upon arriving at the imaging site, participants will complete all relevant consent, demographic, and questionnaire forms. Participants will then undergo a brief sensory testing session, using the Medoc Pathway system, to assess the temperature at which each individual first feels pain (pain threshold). All sensory testing will occur with a thermode placed on the left volar forearm.

A subject is eligible to continue to complete one or two EEG study visits once the study team confirms that the subject's warmth detection (WDT) and heat pain thresholds (HPT) are in the range of normal values (WDT of less than 39°C, HPT between 41 and 47°C) and that the subject has a pain reaction to capsaicin cream. The EEG study visit(s) consist of a sequence of resting state EEG sessions. During all resting state sessions, moment to moment fluctuations in pain ratings will be collected in order to test their relationship to peak alpha frequency.

Subjects will then complete two separate EEG visits; all visits (V0-V2) are separated by at least three weeks. Using a 64-channel EEG system, peak alpha frequency will be measured while participants undergo a baseline, pain-free resting state (no stimulation), an acute pain resting state, a return from pain resting state, and a neuropathic-like pain resting state. During all resting state sessions, moment to moment fluctuations in pain ratings will be collected in order to test their relationship to peak alpha frequency.

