Condition 3: neuropathic-like pain. A topical application of 10% capsaicin cream will be placed on the participant's left volar forearm and covered with a Tegaderm bandage. A 40°C thermode will be placed directly on top of the capsaicin, and incubation will occur for twenty minutes. 40°C is confirmed as a temperature below the participant's pain threshold at V0. A five minute resting state EEG session follows incubation.

Condition 4: return to baseline. Following completion of the acute pain and neuropathic-like pain conditions, an ice-pack will be placed directly over the recently stimulated skin. The icepack will be held in place for five minutes. Pain ratings will be assessed to ensure that pain reports return to baseline levels. Following five minutes of icepack application, the ice pack will be removed and the thermode placed on the skin at skin temperature.

5. Relevant prior experience and gaps in current knowledge

While a simple EEG-based test could provide a useful diagnostic tool for assessing pain objectively, no study to date has evaluated this potential in a systematic way. Here we propose to build on our ongoing work to develop a reliable and simple measure of pain.

6. Background, rationale, and significance, and supporting literature

Neurophysiological investigations of pain have suggested that peak alpha frequency might provide a means of objective pain assessment. In healthy subjects, increased peak alpha frequency is strongly correlated with pain self-reports after exposure to acute noxious heat (*Nir et al., 2010*). Conversely, chronic pain patients compared to healthy control display decreased peak alpha frequencies higher in alpha power (*Sarnthein et al., 2006*). Measures of peak alpha frequency also show a negative

Date: 6/6/2018

Principal Investigator: [name].

Application Number: HP-00064214

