Individuals who meet the inclusion criteria will be scheduled for Visit 0. Study enrollment occurs when a participant arrives at Visit 0. The first 60 participants will complete Visits 1 and 2, while the remaining participants will only complete Visit 2. Visit 1 occurs at least 3 weeks after Visit 0 and Visit 2 occurs at least 3 weeks after Visit 1.

Visit 0:

The following procedures and assessments will be conducted at Visit 0:

1. Obtain informed consent
2. Perform urine screening for toxicology (random selection)
3. Urine pregnancy test (females only)
4. Administer health history form and review eligibility criteria, complete and sign eligibility form
5. Administer questionnaires (STAI-T, STAI-S, SCQ, BDI, EHI, BIS-11)
6. Pain scale training on COVAS
7. Quantitative Sensory Testing (QST) thermal threshold/supra-threshold testing (see below for details)
8. Offset analgesia test (see below for details)
9. Administer post-pain questionnaires (PCS, SFMPQ)
10. Ice pack application – total of 5 minutes or until pain = 0 for 60 seconds
11. Capsaicin application and incubation
12. Brush allodynia test and flare mapping
13. Ice pack application – total of 5 minutes or until pain = 0 for 60 seconds
14. Payment form completion
15. Schedule Visit 1

Visit 1:

The following procedures and assessments will be conducted at Visit 1:

1. Perform urine screening for toxicology (random selection)
2. Urine pregnancy test (females only)
3. Review eligibility criteria, complete and sign eligibility form

Date: 6/6/2018

Principal Investigator: [name].

Application Number: HP-00064214

4. Administer questionnaires (STAI-T, STAI-S, SCQ, BDI, EHI, BIS-11)
5. Pain scale training on COVAS
6. EEG cap setup
7. Quantitative Sensory Testing (QST) thermal threshold/supra-threshold testing (see below for details)
8. Offset analgesia test (see below for details)
9. Ice pack application – total of 5 minutes or until pain = 0 for 60 seconds
10. Resting state EEG runs (acute series):
 - a. 1 minute eyes open resting state
 - b. 1 minute eyes closed resting state
 - c. Baseline-acute resting state – 5 minutes (baseline thermode on)
 - d. Painful-acute resting state – 5 minutes
 - e. Administer post-pain questionnaires (PCS, SFMPQ)
 - f. Ice pack application – total of 5 minutes or until pain = 0 for 60 seconds (no EEG recorded)
 - g. Acute-return baseline resting state – 5 minutes
11. 5 minute break
12. Resting state EEG runs (chronic series):

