with at least 30 seconds between trials, and the thermode is moved to a different position on the forearm/face/neck for each trial. The T1 and T2 durations for the three trials are: 4s/5s, 7s/4s, 5s/6s. We will subsequently test for offset analgesia at each body site while a second stimulus is simultaneously applied to another body site. This will be done for the following combinations of body sites: arm/face, left arm/right arm. Participants will be instructed to rate the pain intensity at one of the two sites using the COVAS.

Test for Brush Allodynia. This test is performed last, after incubation at V0 and after rekindle at V1 and V2. The capsaicin cream and film cover are removed, and the arm area is cleaned with alcohol and the original 1 inch square site is marked. The area of secondary hyperalgesia on the participant's arm is measured with a foam paintbrush dragged at 1 cm per second along four linear paths arranged vertically and horizontally around the marked capsaicin site. Brush stimulation from each direction is started outside the hyperalgesic area, and continued towards the marked square until the participant reports a change in sensation ('burning', 'tenderness', 'pain'). The border is marked on the skin with a marker from each direction. Finally the flare outside the capsaicin site is traced on transparency paper.

EEG

The EEG session will last about 2 hours and will include the following runs: 1 minute open eyes resting state, 1 minute closed eyes resting state, 5 minutes run of baseline-acute resting state, 5 minute run of acute-painful resting state, 5 minute run of acute-return baseline resting state, 15 minute run of capsaicin cream incubation, , 5 minute run of chronic-painful resting state, and 5 minute run of chronic-return baseline resting state, 5 minute run of chronic-painful resting state (rekindle).

Urine Screening

Urine screening will be decided randomly, by allowing the participant to choose 1 of 10 envelopes that s/he opens to reveal his or her assignment. 9 of the envelopes contain a paper that says 'No' to indicate no urine test and 1 envelope contains a paper that says 'Yes' to indicate a urine test will be conducted. Urine samples will be collected and immediately discarded after screening for drug toxicology. A urine sample for toxicology screening testing will be collected in a urine collection cup. The toxicology screening will be performed using Instant-View 12 Panel Drug Tests.

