Data preprocessing for all resting state scans will proceed as follows: data will be re-referenced to the average of the two ear electrodes, band-pass filtered, removed of obvious non-brain (i.e. movement) artifacts, and epoched into 4 second segments. Following preprocessing, a fast fourier transform will be applied to each epoch. The resulting spectral information will then be averaged across epochs. This spectral information will then be exported to Matlab where it will be analyzed with custom scripts developed in our laboratory. Activity in the alpha frequency band (8-12hz) will serve as the primary frequency band of interest.

Interim Data Analysis

Following acquisition of five full data sets, preliminary analyses will occur to assess the primary study outcomes and provide an opportunity to modify the protocol if necessary.

Aim 1. To determine how the experience of innocuous and noxious stimulation affects alpha activity.

Date: 6/6/2018

Principal Investigator: [name].

Application Number: HP-00064214

First, to identify the potential mechanisms that may drive modulations of alpha frequency under painful conditions, we will compare both the acute pain and neuropathic-like pain state scans against the most temporally proximate innocuous state scans. Each pain state will be compared to the baseline scan directly preceding it, and the differences between acute pain and warm and neuropathic-like pain and warm will be compared.

Second, we will compare the spectral characteristics of acute pain and neuropathic-like pain in the alpha frequency band and determine the ability of alpha frequency measures distinguish these two pain states. Each pain state will be compared to the baseline scan directly preceding it, and the differences between acute pain and warm and neuropathic-like pain and warm will be compared.

Aim 2. To assess the test-retest reliability of the alpha frequency as an objective measure of pain in two different experimental pain states (acute and neuropathic-like).

Here, we will identify the degree to which alpha frequency under various pain states remains constant across this time. This will be accomplished by comparing the resting states, and the differences between them, across testing sessions. If alpha frequency observations remain stable, within an individual, across testing sessions, this will provide important evidence that alpha frequency, and how it shifts, may represent an individually based characteristic or biomarker.

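### Aim 1 compares each pain scan only with the innocuous scan before it, although a return scan follows each pain state, so session drift cannot be separated from a pain effect

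*Combined protocol and SAP*

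**What the plan says.** Section 4 lists, after the pain-free baseline, "an acute pain resting state, a return from pain resting state, and a neuropathic-like pain (ongoing pain) resting state". Condition 4 of that section applies to both pain types: "Following completion of the acute pain and neuropathic-like pain conditions, an ice-pack will be placed directly over the recently stimulated skin". Recovery is checked there on ratings: "Pain ratings will be assessed to ensure that pain reports return to baseline levels". Nothing comparable is stated for alpha.

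Section 9 schedules the return scans. After the acute series, step 10g is "Acute-return baseline resting state – 5 minutes". After capsaicin pain and ice there is another 5-minute return scan, followed by a rekindle pain scan. The visit lists give this second return scan the acute label; the EEG paragraph calls it "5 minute run of chronic-return baseline resting state".

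Section 18, Aim 1 opens by setting the pain scans "against the most temporally proximate innocuous state scans", then narrows this in the next sentence: "Each pain state will be compared to the baseline scan directly preceding it". The narrowing is repeated for the second analysis, which adds that "the differences between acute pain and warm and neuropathic-like pain and warm will be compared". Section 18 names no return scan, no contrast with one, and no adjustment for time or order.

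**The concern.** The recorded sequence is innocuous, pain, innocuous, but the planned contrast uses only the first step. In the acute and first capsaicin contrasts, pain is therefore fully confounded with elapsed time. Drift is plausible from the protocol's own description: scans are made with eyes closed in a dark room, participants are told to stay awake, the EEG session lasts about two hours, and the acute series always comes first.

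The stated purpose is an objective measure of pain. Such a measure should change when pain begins and move back, at least in part, when it ends. The plan records the scans that could show this but does not say they will be compared. Because the two series also have unequal gaps, drift does not cancel when the acute change is compared with the neuropathic-like change. Aim 2 does not help: a drift that recurs at each visit would look like a stable individual shift.

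**Working it through.** The plan gives no figure for drift, scan noise or a paired difference. Section 17 sizes a correlation, so there is nothing on this point to reproduce. The check uses scheduled times.

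**Inputs (Section 9, visit lists).** EEG scans 5 min; incubation 20 min; break before the chronic series 5 min; ice taken as 5 min; rests and questionnaires set to 0. The preceding gaps are therefore minimum values. The EEG paragraph gives 15 min of incubation, so both are shown. A baseline-chronic scan is listed at Visit 2 only; at Visit 1 the last innocuous scan before capsaicin is 10g.

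**Scan midpoints (minutes from the start of the preceding scan).**

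| Contrast | Preceding | Pain | Return | Preceding to pain | Pain to return |
|---|---|---|---|---|---|
| Acute | 2.5 | 7.5 | 17.5 | 5 | 10 |
| Capsaicin, Visit 2 | 2.5 | 27.5 | 37.5 | 25 (20 with 15 min incubation) | 10 |
| Capsaicin, Visit 1 | 2.5 | 32.5 | 42.5 | 30 (25 with 15 min incubation) | 10 |

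**What each contrast measures.** Let P be the pain effect, f the share of it still present in the return scan, and d a linear drift per minute.

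- Pain minus preceding: P + 5d (acute); P + 25d (Visit 2 capsaicin).
- Pain minus return: P(1 − f) − 10d in both.
- Return minus preceding: fP + 15d (acute); fP + 35d (Visit 2 capsaicin).

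Drift enters the first two with opposite signs, which is why the return scan is informative.

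**Difference of differences (planned contrasts).** Visit 2: 25d − 5d = 20d. Visit 1: 30d − 5d = 25d. With 15 min incubation: 15d and 20d.

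**Rekindle.** The chronic-return scan directly precedes it, with a midpoint gap of at least 2.5 + 2.5 = 5 min. A shift persisting from the first capsaicin scan is in both scans and cancels; 5d of drift remains.

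**Bracketed contrast.** Pain − [(1 − w) × preceding + w × return], with w = (preceding-to-pain gap) / (preceding-to-return gap). Acute: w = 5/15 = 1/3. Visit 2 capsaicin: w = 25/35 = 0.71. Visit 1: w = 30/40 = 0.75. Linear drift cancels. An unweighted mean of the two innocuous scans would leave −2.5d, 7.5d and 10d.

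**Its price.** With equal, independent scan noise, the variance is 1 + (1 − w)² + w²: 1.556 (acute) and 1.592 (Visit 2 capsaicin), against 2. The SE ratios are √(1.556/2) = 0.882 and √(1.592/2) = 0.892. The contrast estimates P(1 − wf), so it loses power against the planned one once wf exceeds 1 − SE ratio: f > 0.108/0.714 = 0.15 for capsaicin, and f > 0.118/0.333 = 0.35 for acute.

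**Illustration only.** Assume no pain effect and a drift bias of b SDs of the paired difference. A two-sided 5% paired t test (noncentrality b√N) rejects as follows; 108 is 120 less the 10% capsaicin non-response in Section 17.

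| b (assumed) | N = 120 | N = 108 |
|---|---|---|
| 0.1 | 19% | 18% |
| 0.2 | 58% | 54% |
| 0.3 | 90% | 87% |

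**The case against.** Several objections have force.

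- **The return scans are not idle.** 10g is the comparator for capsaicin at Visit 1, the chronic-return scan precedes rekindle, and Aim 2 compares resting states across visits for the first 60 participants. A reader might infer that these scans have no role; that would be wrong. In none of these uses, however, is a pain scan or its baseline compared with the return scan that follows. Rekindle comes closest, and there a lasting after-effect is separated from pain tracking.
- **The opening sentence of Aim 1 is wider.** By midpoints, the innocuous scan nearest to Visit 2 capsaicin pain is the return scan (10 against 25 min). The next sentence limits the comparison to the preceding scan, so the two sentences point to different scans there. The narrower one is stated twice.
- **Section 4 plans to relate ratings to peak alpha frequency in all resting states**, which would include return scans. Section 18 gives no analysis for it.
- **One steady drift cannot explain everything.** The background reports higher peak alpha frequency with acute heat pain and, with capsaicin, lower frequency at greater pain. A one-way drift cannot produce shifts in both directions, so it does not follow that any change over the session would be credited to pain. Drift could still create or mask either contrast alone and bias their difference.
- **The return scan is not a clean baseline.** It follows ice, and capsaicin is removed only after rekindle. A reader might infer that the bracketed contrast should replace the planned one. With a weight of 0.71 on that scan and a power loss once about 15% of the effect persists, the documents do not support that.

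**Conclusion.** The point holds as a gap in the analysis plan, not as a flaw in the data collected. The acute and first capsaicin contrasts cannot separate a pain effect from session drift over at least 5 min (acute) and 25 min (Visit 2 capsaicin, 20 min incubation). The Visit 2 acute-versus-neuropathic comparison keeps 20 min of that drift. These gaps rest on the schedule alone.

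How much this matters numerically is unknown. The documents give no drift rate, shape or SD, so the rejection rates above show only sensitivity to an assumed bias. A reader might infer that Aim 1 will produce false findings; the documents do not show that.

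The return scan does not settle everything either. Within one series, two independent contrasts cannot identify P, f and d together, so a return scan that stays shifted may reflect drift, an after-effect or both. That argues for reporting the contrasts jointly, not for a rule that a shift counts as pain-related only if alpha moves back. This is a cheap improvement that changes what Aim 1 can conclude.

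**What to change.** In Section 18, Aim 1:

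1. Keep the planned contrast with the preceding baseline.
2. For each series, add a pain-versus-return and a return-versus-baseline contrast, with confidence intervals. Alternatively, fit one repeated-measures model to the baseline, pain and return scans with a time term. Within one series, such a model must treat baseline and return as the same innocuous state, because three separate scan levels and a linear time term cannot all be estimated.
3. Report the time-weighted bracketed contrast as a sensitivity analysis. Nominal weights on preceding and return scans are 2/3 and 1/3 (acute), and 0.29 and 0.71 (Visit 2 capsaicin with 20 min incubation).
4. Describe a shift as tracking pain only in light of these contrasts together.
5. Report pain ratings in the return scans, and show results with and without participants whose return scan was not pain-free.

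The documents should also reconcile the 15- and 20-minute incubation entries and the baseline-chronic scan listed only at Visit 2, since these set the comparator and the gaps.

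Cost: plan wording, a few script lines and a few more reported analyses; no new data. Downside: after-effects of capsaicin or ice can shrink the return contrasts, so lack of full reversal does not by itself rule out a pain effect, and the write-up should say so.

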Neurophysiological investigations of pain have suggested that electroencephalographic (EEG) measures of peak alpha frequency might provide a means of objective pain assessment. In healthy subjects, increased peak alpha frequency is strongly correlated with pain self-reports after exposure to acute noxious heat. Conversely, chronic pain patients compared to healthy control display decreased peak alpha frequencies higher in alpha power. Measures of peak alpha frequency also show a negative relationship with disease duration (de Vries et al., 2013), suggesting that peak alpha frequency may not only index ongoing pain but also disease progression.

While a simple EEG-based test could provide a useful diagnostic tool for assessing pain objectively, no study to date has evaluated this potential in a systematic way. Here we propose to build on our ongoing work to develop a reliable and simple measure of pain. Our overall aim is to determine the predictive accuracy, reliability, and specificity of EEG alpha activity in acute pain and a model of neuropathic pain in healthy subjects.

3. Purpose/specific aims/objectives and hypothesis

Our overall aim is to determine the predictive accuracy, reliability, and specificity of EEG alpha activity in acute pain and a model of neuropathic pain in healthy subjects.

Aim 1. To determine how the experience of innocuous and noxious stimulation affects alpha activity and whether alpha activity can predict acute and neuropathic-like pain.

Aim 2. To assess the test-retest reliability of the alpha frequency as an objective measure of pain in two different experimental pain states (acute and neuropathic-like).

If our approach is successful it would be a major step forward to providing an objective measurement of pain. This approach could be adopted by other laboratories to test on multiple chronic pain populations. Once we have optimized the procedure, the setup could be simplified to only include a few recording electrodes and would thus be a relatively quick method. Future work would also include testing the effects of analgesics versus placebo in healthy subjects, as well as in chronic pain patients, to determine whether this method could provide a sensitive test of drug efficacy that would not rely on subjective ratings.

[figure not shown]
4. Research design

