Participants will be numerically coded upon enrollment. Only the team members directly involved with the participants will have access to their names, and once a participant has completed the study, only numerical codes will be used. The original list with the codes and names will be securely locked.

Date: 6/6/2018

Principal Investigator: [name].

Application Number: HP-00064214

Identifiable data will be kept in the PI's office. Coded data will be kept on a central server that can only be accessed by research team members (password protected).

Identifiable data will be kept in a locked filing cabinet.

The PI will have access to identifiable data. Only research team members will have access to coded data.

15. Data and safety monitoring plan

Data Safety Monitoring by the PI and reported to the IRB semi-annually.

The PI will take note of any unexpected risks or harm to the participants and report them to the IRB and the sponsor, Purdue Pharma LP.

Data to be reviewed include enrollment, adverse events, unanticipated events, and preliminary analyses.

Participants will be asked to contact a study team member to report unanticipated events or potential adverse events.

16. Payment

For their time, participants will be compensated \$25 for the eligibility screening visit and \$75 per EEG visit. Payments will be made by check.

17. Sample size calculation

The target sample size for this study is 120 healthy male and female subjects. This number is based on our preliminary data and accounts for variability in the response to capsaicin (about 10% of people do not react to topical capsaicin). Additionally, this sample size is sufficiently powered to capture a moderately size relationship ($r > .3$) between pain and peak alpha frequency, according to a correlation power analysis with a Type I error rate of .05 and a Type II error rate of .2. The sample size is also sufficient for performing multivariate analyses, which will allow us to develop data-driven algorithms for pain sensitivity.

18. Data analysis plan

Data Analysis Approach

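### The Section 18 analysis meant to show how well alpha activity distinguishes acute from neuropathic-like pain specifies only comparisons, and so gives no measure of how accurately an individual's pain state is identified.

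*Combined protocol and SAP*

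**What the plan says.** Section 3 states that the overall aim is to "determine the predictive accuracy, reliability, and specificity of EEG alpha activity". Its wording of Aim 1 also asks whether alpha activity can predict the two kinds of pain. When Section 18 restates Aim 1, the prediction clause is absent.

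Section 18 then gives two analyses for Aim 1.

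- **First:** both pain scans are set against the nearest innocuous scans, to look at mechanisms.
- **Second:** the alpha-band spectra of the two pain states are compared, and the analysis is to "determine the ability of alpha frequency measures distinguish these two pain states".

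Both paragraphs close with the same sentence. Each pain state is set against its preceding baseline, and "the differences between acute pain and warm and neuropathic-like pain and warm will be compared".

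Neither Section 18 nor any other section names an AUC, sensitivity, specificity, classification rate, cut-off or validation scheme. Section 17 says the sample size also suffices for multivariate analyses, "which will allow us to develop data-driven algorithms for pain sensitivity", without a method or a performance measure.

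**The concern.** Comparing two sets of shifts asks whether alpha moves differently, on average, in the two pain states. Distinguishing the states asks how often the alpha shift would point to the right state in a given person. With around a hundred participants the first answer can be a clear yes while the second is little better than guessing.

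What is at stake is the wording of the conclusion. The study is presented as a step towards an objective measure of pain, and a report that alpha distinguishes the two states would be taken as evidence on that. The plan does not fix which quantity would support such a statement. Section 18 also allows the protocol to be modified after a preliminary look at five full data sets, which is a further reason to settle the measure in advance.

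**Working it through.** **The plan's own figure.** Section 17 states: "The target sample size for this study is 120 healthy male and female subjects". It calls this "sufficiently powered to capture a moderately size relationship ($r > .3$) between pain and peak alpha frequency". The stated significance level is .05, and the stated Type II error of .2 corresponds to 80% power. The Fisher z formula, two-sided, gives

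N = ((1.960 + 0.842) / atanh(0.3))² + 3 = (2.802 / 0.3095)² + 3 = 84.9, so 85.

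Allowing for 10% loss, 85 / 0.90 = 94.4, so 95. The formula does not return 120, but Section 17 says the number also rests on preliminary data and claims only sufficiency. That claim is correct: power for r = 0.3 is 91.7% at 120 and 88.7% at 108. However, this calculation concerns a correlation between pain and alpha and says nothing about separating the two pain states.

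**Inputs for the check.**

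- Evaluable number: Section 17 says "about 10% of people do not react to topical capsaicin", so 120 × 0.90 = 108.
- Test: a two-sided paired t-test at .05 on the difference between each person's two baseline-adjusted shifts. This is an assumption, because the plan says only that differences will be compared. Both pain states are recorded in each EEG visit, so the contrast is within person.
- Correlation ρ between the two shifts: not in the documents. It is taken over 0 to 0.9, with normality and equal variances assumed.

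**Step 1: smallest significant effect.** With d_z the mean difference between the two shifts divided by the standard deviation of that difference,

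d_z = t(.975, 107) / √108 = 1.982 / 10.392 = 0.191.

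**Step 2: effect detectable with 80% power.** Solving the noncentral t equation at n = 108 gives d_z = 0.272.

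**Step 3: share of people whose two shifts differ in the expected direction.** This is Φ(d_z).

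- Significance limit: Φ(0.191) = 0.576.
- 80%-power effect: Φ(0.272) = 0.607.
- Chance: 0.50.

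**Step 4: AUC for telling an acute shift from a neuropathic-like shift.** If each shift has standard deviation σ, the difference has standard deviation σ√(2(1−ρ)). The separation in units of σ is then d = d_z√(2(1−ρ)), and AUC = Φ(d/√2) = Φ(d_z√(1−ρ)).

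| ρ (assumed) | AUC at significance limit | AUC at 80%-power effect |
|---|---|---|
| 0 | 0.576 | 0.607 |
| 0.5 | 0.554 | 0.576 |
| 0.8 | 0.534 | 0.548 |
| 0.9 | 0.524 | 0.534 |

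**Step 5: sensitivity to n.** With all 120 evaluable, the limits are d_z = 0.181 (57.2%) and 0.258 (60.2%). With 80 evaluable, the significance limit is 1.990 / √80 = 0.223 (58.8%).

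**For scale.** An AUC of 0.70 would need d_z = 0.524 / √(1−ρ): about 0.52 at ρ = 0, 0.74 at ρ = 0.5 and 1.17 at ρ = 0.8. All are well above the effect at which the test becomes significant.

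**The case against.** The best defence has four parts.

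- **The Second analysis is not simply a copy of First.** Only the closing sentence is repeated; the lead-in adds a direct comparison of the two states' spectra. A reader might infer that the two analyses are the same throughout. The text does not support that, and the repetition may be a drafting slip. The added step is still a comparison, however, and yields no accuracy.
- **No test is named.** A reader might infer that the plan commits itself to a wrong analysis. It does not: it commits to determining the ability to distinguish and leaves the measure unstated. The paired mean test used above is the natural reading, not the plan's wording.
- **Separating acute from neuropathic-like pain is one part of the aim.** The study also relates continuous pain ratings to alpha and examines test-retest reliability. A reader might infer that the whole study fails to address its purpose; that goes too far. The multivariate algorithms in Section 17 do not fill the gap, since they target pain sensitivity and carry no performance measure.
- **Nothing in the documents makes a p-value a licence for diagnostic use.** This is a study of healthy volunteers, Section 3 leaves wider application to later work, and an AUC could be computed from the planned recordings at any time. This limits the seriousness. It does not remove the case for fixing the measure before the results are seen.

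The 108 is also generous. Participants are enrolled at Visit 0, and threshold screening, toxicology failures and dropout come on top of capsaicin non-reaction. Fewer participants raise the significance limit, but only slightly over the range checked.

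**Conclusion.** The gap is real and should be fixed. Followed as written, the Second analysis compares the two pain states without measuring how well an individual's state is identified, although predictive accuracy and specificity are the declared aim.

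Read as a paired mean test at about 108 evaluable, significance is reached when about 58% of people have shifts differing in the expected direction; at the 80%-power effect it is about 61%. The corresponding AUC ranges for baseline-adjusted shifts are 0.52–0.58 and 0.53–0.61. A significant contrast is therefore compatible with weak discrimination. It does not imply it, because a large effect would be significant too.

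The shares rest on n, normality and the assumed test. The AUC ranges also rest on equal variances and an assumed ρ of 0 to 0.9. A reader might infer one AUC of about 0.55, or an AUC for single scans. The documents support neither: they give no correlation, and the plan references each pain state to its own baseline, so a single-scan figure would need correlations among four scans.

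**What to change.** Under Second, replace the repeated sentence with a discrimination analysis of the baseline-adjusted alpha shifts:

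1. The share of participants whose acute and neuropathic-like shifts differ in a direction stated in advance, with a 95% confidence interval.
2. The AUC for acute versus neuropathic-like pain, and for each pain state versus its innocuous scan. Confidence intervals should be bootstrapped by participant, which also keeps together the two EEG visits of the first 60 participants.
3. If an algorithm is trained, training and testing data split by participant.

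Base any statement that alpha distinguishes the states on these estimates and their intervals, and report the mean contrast as supportive.

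Precision would be useful at the planned size. At n = 108 the approximate 95% half-width of an AUC is 0.077 at 0.55 and 0.069 at 0.70 (Hanley-McNeil, treating the states as independent).

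The cost is a change of wording and slightly more analysis, with no new participants, visits or recordings. The drawback is that the result may look less favourable than a p-value.
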